7.5.3. ECG

The ECGs will be assessed by the investigator and deemed “Normal”, “Abnormal, not clinically significant” and “Abnormal, clinically significant” and tabulated by visit and treatment group.

In addition, the numerical ECG data generated by the central ECG laboratory will be summarized by descriptive statistics for each parameter by visit and treatment group. Also the changes from baseline will be summarized.

The QTc intervals fulfilling the following criteria will be tabulated separately using Fridericia’s correction:

- Values >500 msec
- Values increasing >15% from baseline if baseline value is ≥ 440 msec
- Values increasing >30% from baseline if baseline value is <440 msec

- Values increasing >30 msec from baseline
- Values increasing >60 msec from baseline.

7.5.4. Physical Examination

Abnormal physical examination findings will be listed and summarized by visit and treatment group. The abnormal values will be further classified as clinically significant and not clinically significant based on the investigator's interpretation. In addition to the summary, all abnormal findings classified as clinically significant will be listed.

8. EFFICACY

8.1. General

For the efficacy endpoints, continuous data will be summarized at each protocol scheduled visit, by treatment regimen, using summary statistics. Actual values and changes from baseline will be presented. All categorical endpoints will be summarized at each protocol scheduled visit, by treatment regimen, using frequency tabulations.

As the primary and secondary purpose of this study is to explore the 2 treatment regimens with regards to safety and efficacy and not to perform confirmatory analyses comparing the treatment regimens, there will be no formal hypothesis testing performed and adjustments for multiplicity are not required.

The analyses of the efficacy data will focus on estimating the changes from baseline of the present study for cohort 2 and from baseline of 006 study for cohort 1. Cohort 1 and Cohort 2 will be analyzed separately and combined. Data from Cohort 2 will be summarized by treatment group (Regimen 1 or Regimen 3), i.e. the summaries of efficacy data will include the following groups: Cohort 1/Regimen 1, Cohort 2/Regimen 1 and Cohort 2/Regimen 3. For the combined cohort analysis Regimen 1 and Regimen 3. The mITT set will be used for all efficacy analyses.

Sensitivity analyses of efficacy data will be conducted by excluding the patients who were randomized to receive Regimen 2. These analyses will be done for the “ON” time without troublesome dyskinesia.

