9.2 Treatment Period

9.2.1 Day 1 (Baseline Visit and Start of Treatment)

For subjects in Cohort 1 rolling-over directly, the Baseline visit can be conducted together with the Day 28 visit in study ND0612H-006. For Motor (UPDRS part III), the last assessment performed on Day 28 of study ND0612H-006 will be used as baseline assessment for the current study. The results of the ECG performed at Day 28 of the ND0612H-006 study must be reviewed during the baseline visit of the ND0612H-012 study to ensure no exclusionary abnormalities are present.

The following **Baseline assessments** will be performed:

Subjects in Cohort 1 will provide informed consent at Day 1 and will be provided with the "ON/OFF" diaries and with training on the use of the home diary. The Baseline "ON/OFF" assessment for Cohort 1 will be performed on Days 2 and 3. The subsequent "ON/OFF" diary assessments will be completed 2 days prior to each subsequent visit.

Up to 08 December 2016, subjects in Cohort 2 were randomized to Regimen 1 or 2 at a 1:1 ratio. After this date (pending implementation of Protocol Amendment 1), all subjects on Regimen 2 were switched to Regimen 1. After implementation of Protocol amendment 2, all subjects in Cohort 2 will receive Regimen 3.

The following procedures will be conducted for ALL subjects:

- Reassessment of eligibility against inclusion/exclusion criteria
- Review of concomitant medication (including anti-PD medication)
- Urine pregnancy test for female subjects of childbearing potential
- Vital signs (including supine [after resting for at least 5 min] and standing BP, pulse rate, and body temperature
- Body weight
- Safety laboratory tests, including blood chemistry, hematology, and dipstick urinalysis (see Section 10.1.2 for details)
- Physical and neurological examination
- Assessment of suicidality using C-SSRS (see Section 10.1.8 and Appendix 17.3)

- Assessment of impulsive-compulsive disorders in PD using the QUIP-RS (see Section 10.1.10 and Appendix 17.4)
- Assessment of excessive daytime sleepiness using ESS (see Section 10.1.9 and Appendix 17.5)
- PD rating using UPDRS Parts I, II, III and IV (see Section 10.2.1.2 and Appendix 17.6)
- Completion of the PDQ-39 (QoL) (see Section 10.2.1.5 and Appendix 17.7)
- Completion of the EQ-5D-5L (QoL) (see Section 10.2.1.6 and Appendix 17.8)
- Assessment of sleep using the PDSS (see Section 10.2.1.4 and Appendix 17.9)

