11 STATISTICAL METHODS

11.1 Statistical and Analytical Plans

The analyses related to the primary objective will include the study data up to the Month 12 visit. A separate analysis will be conducted based on the data up to 102 months. In addition, safety snapshot data in between the above-mentioned time periods may be summarized during the study conduct for regulatory purposes.

The analysis of the safety data will be based on data accumulated from the present study. For safety, Cohort 1 and Cohort 2 will be analyzed jointly (for Regimen 1) and separately. For efficacy, Cohort 1 and Cohort 2 will be analyzed separately (where applicable). Baseline values for Cohort 1 will be derived from the ND0612H-006 study.

The safety data will be summarized for both the total Safety Set and broken down by the treatment regimen (Regimen 1 or Regimen 3). An additional safety analysis will be conducted by excluding the safety data from the subjects who received Regimen 2 during the corresponding treatment period (i.e., the data captured after the first dose of Regimen 2 until the switch to Regimen 1 will be excluded).

A fully detailed Statistical Analysis Plan (SAP) will be produced and finalized after finalizing the protocol and before any data base lock. The SAP will detail the implementation of all the planned statistical analyses in accordance with the protocol. Any deviations from the statistical analyses planned in the protocol will be documented in the SAP and any deviations from the statistical analyses planned in the SAP will be documented in the final clinical study report.

All data will be listed. In general, data will be summarized using either descriptive statistics (number of non-missing observations, mean, median, standard deviation (SD), standard error of the mean (SEM), minimum and maximum for continuous data) or frequency counts and percentages for categorical data.

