5.2. Baseline Definition

In general, Baseline will be defined for each subject as the last available, valid, non-missing assessment before the start of first study drug (ND0612) administration within the current study (ND0612H-012) or before the start of first study drug administration in study ND0612H-006 (for cohort 1). The analyses involving calculation of change from baseline will be based on the actual changes from baseline (not percentage), unless stated otherwise.

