10. CHANGE FROM ANALYSIS PLANNED IN PROTOCOL

- The version of SAP (3.0) was based on Clinical Study Protocol ND0612H-012 Version 8.0 (global Amendment 7): issued on 12 March 2019. At the time when the SAP version 3.0 was finalized, the sponsor endorsed FDA recommendation of a change in the safety primary analyses which were not yet reflected in the protocol. This change was intended to be introduced in a later protocol amendment
- The version of SAP (4.0) was based on Clinical Study Protocol ND0612H-012 Version 9.0 (global Amendment 8): issued on 11 July 2019. There are no changes from this current SAP version (4.0) to the amended protocol (V9.0).

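### SAP 8.1 plans a combined-cohort efficacy analysis by Regimen 1 and Regimen 3; on the non-diary endpoints, whose described model has no cohort term, its natural reading folds any cohort difference into the regimen contrast

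*SAP*

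**What the plan says.** SAP 8.1 (Efficacy, General) states "Cohort 1 and Cohort 2 will be analyzed separately and combined". It lists the summary groups as "Cohort 1/Regimen 1, Cohort 2/Regimen 1 and Cohort 2/Regimen 3" and then adds "For the combined cohort analysis Regimen 1 and Regimen 3". No group combines Cohort 1 with Regimen 3. Section 8.1 also says the analyses focus on "estimating the changes from baseline of the present study for cohort 2 and from baseline of 006 study for cohort 1", and SAP 5.2 sets Cohort 1's baseline "or before the start of first study drug administration in study ND0612H-006 (for cohort 1").

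SAP 8.2.1 gives the one efficacy MMRM for the regimen comparison. Its terms are baseline, regimen, visit and regimen by visit, and it estimates the between-regimen difference at each visit. Its code restricts the data to Cohort 2, and the text explains this by the diaries having been assessed differently in Cohort 1. SAP 8.2.6 (PDQ-39), 8.2.8 (UPDRS II), 8.2.11 (PDSS) and 8.2.12 (UPDRS III) refer back to this model and change only the baseline covariate. They do not say whether the Cohort 2 restriction carries over.

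Protocol 11.1 says "For efficacy, Cohort 1 and Cohort 2 will be analyzed separately (where applicable"). SAP Section 10 says "There are no changes from this current SAP version (4.0) to the amended protocol (V9.0").

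**The concern.** Every Cohort 1 subject in a combined analysis falls in Regimen 1, and Regimen 3 is Cohort 2 only. The cohorts differ in ways that could affect change from baseline:

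- **Selection.** Cohort 1 completed study 006 treatment no more than one month before enrolling (Protocol 8.3.2).
- **Baseline and elapsed time.** Cohort 1 is measured from study 006 and Cohort 2 from the present study, so the same visit label means different times since baseline.
- **Entry to the mITT set.** Cohort 1 qualifies on UPDRS III data and Cohort 2 on diary data (SAP 4.4).

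Without a cohort term, any resulting difference is credited to the infusion regimen. The combined contrast has the most subjects, so it is likely to be read as the most complete regimen comparison, with a nominal p-value under SAP 5.3. Showing the cohorts separately does not correct the combined estimate. The planned sensitivity analysis without subjects randomised to Regimen 2 does not help either: SAP 8.1 limits it to ON time without troublesome dyskinesia, which already excludes Cohort 1.

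**Working it through.** The plan has no power calculation or effect size to reproduce. The check has four steps.

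**1. Which endpoints are exposed.** SAP 3.2.3 marks the diary and EQ-5D-5L as Cohort 2 only. That leaves UPDRS II, UPDRS III, PDQ-39 and PDSS in the MMRM. CGI and SGI-I are only tabulated.

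**2. Timing.** Protocol 9.2.1 ties direct roll-over to the Day 28 visit of study 006, and the gap before enrolment may be up to one month. If Day 28 counts from first dosing, Cohort 1's Month 12 lies at 12 + about 1 + (0 to 1) = about 13 to 14 months after its 006 pre-dose baseline. Its Month 1 lies at about 2 to 3 months.

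**3. Size of the shift.** With no cohort term, at a single visit:

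expected pooled contrast = Cohort 2 contrast + w × d, where w = n(C1) / [n(C1) + n(C2,R1)]

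and d is the mean difference in change between Cohort 1 and Cohort 2/Regimen 1.

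Inputs from the documents: Cohort 1 is at most 36 (Protocol 11.2); the total is about 210 (Protocol 11.2) or 120 to 170 (SAP 3.3). Assumptions, because the documents give no figures: Cohort 1 of 18 or 36, Cohort 2/Regimen 1 of 12 to 40, and d of 0.25 to 0.75 SD.

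| Cohort 1 | C2/Regimen 1 | w | Shift, d = 0.25 SD | d = 0.5 SD | d = 0.75 SD |
|---|---|---|---|---|---|
| 36 | 12 | 36/48 = 0.75 | 0.19 | 0.38 | 0.56 |
| 36 | 40 | 36/76 = 0.47 | 0.12 | 0.24 | 0.36 |
| 18 | 12 | 18/30 = 0.60 | 0.15 | 0.30 | 0.45 |
| 18 | 40 | 18/58 = 0.31 | 0.08 | 0.16 | 0.23 |

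With no true regimen effect and d = 0.5 SD, a normal approximation puts the rate of nominal two-sided p < 0.05 at 13 to 62% over these sizes and totals of 120 to 210. Over d of 0.25 to 0.75 SD it is 7 to 93%. At d = 0 the shift is zero.

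A simulation (4,000 runs, one visit, no baseline covariate, 36 in Cohort 1, 24 in Cohort 2/Regimen 1, total 210, d = 0.5 SD) gave a mean shift of 0.30 SD and a 49% rejection rate. With a cohort term, or with Cohort 2 only, the shift was about zero and the rate 5.0%. The two corrected estimates agreed to rounding error, because Cohort 1 has no Regimen 3 subjects to inform the contrast.

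**4. Loss of precision.** With n = n(C2,R1) and n3 the Regimen 3 group (total minus all Regimen 1), the ratio of standard errors, Cohort 2 only to pooled, is

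√{ [1/n + 1/n3] / [1/(n(C1)+n) + 1/n3] }.

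- Cohort 1 = 36, total 210: n = 12, n3 = 162 gives √(0.0895/0.0270) = 1.82; n = 40, n3 = 134 gives √(0.0325/0.0206) = 1.25.
- Cohort 1 = 36, total 120: n = 12, n3 = 72 gives √(0.0972/0.0347) = 1.67; n = 40, n3 = 44 gives √(0.0477/0.0359) = 1.15.
- Cohort 1 = 18: the ratio runs from 1.11 (total 120, n = 40, n3 = 62) to 1.51 (total 210, n = 12, n3 = 180).

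**The case against.** The strongest reply is that the SAP never writes a combined-cohort MMRM. The sentence on the combined analysis is a fragment, stands next to a list of summaries and mentions no contrast. The only regimen-contrast code is already restricted to Cohort 2, as is the subgroup code in 8.3. This stands in part: the pooled contrast is inferred, and a reader who takes the SAP to specify it outright goes further than the text. But the restriction is justified only by the diaries. Cohort 1's mITT set is built on UPDRS III, and the protocol synopsis extends the MMRM to further endpoints for both cohorts where applicable. The restriction therefore cannot be assumed for the non-diary endpoints.

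A reader might also infer that SAP Section 10 conceals a departure from the protocol. The documents do not support that. Protocol 11.1.4.3 already provides for efficacy summaries of the total mITT set and by regimen. The SAP measures itself against protocol V9.0, while the version available here is V10.0. Nor does the protocol text specify a pooled regimen contrast, so the point remains to be checked.

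It is also fair that the cohorts are not wholly distinct. The exclusion for earlier intolerance of ND0612 applies to both, and Cohort 2 may include earlier ND0612 completers. What is particular to Cohort 1 is recent completion of study 006 and the 006 baseline.

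Finally, efficacy is exploratory, without formal testing or multiplicity control. That limits the consequences but does not remove a bias in an estimate.

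**Conclusion.** The concern holds for UPDRS II, UPDRS III, PDQ-39 and PDSS. On the natural reading of SAP 8.1 and 8.2, the combined Regimen 1 versus 3 contrast carries w × d, with w about 0.31 to 0.75 under the assumed group sizes. The documents give neither the size nor the sign of d, so the shifts above are illustrations and not estimates.

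The Cohort 1 baseline for UPDRS III adds uncertainty. SAP 5.2 and 8.1 place it before first dosing in study 006, whereas Protocol 9.2.1 says, for direct roll-over, "the last assessment performed on Day 28 of study ND0612H-006 will be used as baseline assessment for the current study", a visit at the end of 006 treatment. The choice could change both the size and the sign of d.

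Two wider inferences are not supported. The ON/OFF diary results are not biased by this, because Cohort 1 is excluded from them. And the Cohort 2 contrast is not a randomised comparison: Regimen 3 was assigned to new Cohort 2 subjects after Protocol amendment 2, so regimen is confounded with enrolment period there too. Given the exploratory status, this is a change that should be made, but it does not threaten the primary safety objective.

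**What to change.** - In SAP 8.1, 8.2.6, 8.2.8, 8.2.11 and 8.2.12, state that every Regimen 1 versus 3 contrast comes from Cohort 2 only, and write the `COHORT=2` condition explicitly for each endpoint.
- Label that contrast non-randomised, because regimen followed the amendment date.
- Present pooled Regimen 1 results as descriptive within-regimen summaries, with no between-regimen contrast or p-value.
- Reconcile the Cohort 1 UPDRS III baseline between SAP 5.2/8.1 and Protocol 9.2.1.
- Check the combined analysis against protocol V9.0 and list it in SAP Section 10 if it is an addition.

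Adding cohort and cohort-by-visit terms to a pooled model is possible but gives essentially the same contrast, so it buys no precision.

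The drafting cost is a few lines. The statistical cost is that the contrast has Cohort 2-only precision: its interval is roughly 15 to 82% wider than the pooled one with 36 Cohort 1 subjects, or 11 to 51% wider with 18, under the assumed sizes.

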8.2 Discussion of Study Design

An open-label design in which subjects are randomized to 1 of 2 treatment regimens (Cohort 2) or continue on 1 of these regimens (Cohort 1) from a previous clinical study (ND0612-006) was chosen for this Phase IIb safety study.

Following the recommendation of the ND0612-006 oversight committee the sponsor decided to discontinue Regimen 2 treatment on 08 December 2016. The decision was based on interim data from ND0612-006 that suggested that Regimen 2 (14 hr at a rate of 0.64 mL/hr) is suboptimal in respect to the therapeutic response as reflected by the daily "OFF" time, and therefore assessment of its long-term safety is not relevant. The sponsor decided to further evaluate an optimized daily treatment regimen of 16 hr at a rate of 0.75 mL/hr, and introduced treatment Regimen 3 in Protocol amendment 2.

Clinical studies have demonstrated that ND0612, at concentrations of up to 60 mg/mL LD and 14.0 mg/mL CD, can be administered for a continuous 24 hr period in healthy subjects and patients with PD and produce clinically relevant plasma concentrations of LD and CD with modest intersubject variability. This appears to be accomplished with minimal local dermal toxicity and with only mild and expected systemic toxicity. Total daily doses of ND0612 over 24 hrs have ranged to as high as 720 mg LD and 90 mg CD in study ND0612H-005, which was well-tolerated without significant AEs. This exposure is the same as the planned daily exposure of 720 mg LD/90 mg CD over 24 hrs in the current study for Regimen 1. Based on clinical experience so far, the local infusion site safety profile of ND0612 is favorable, local transient findings do generally not impact the subjects' general well-being and the drug's tolerability.

The variables used for assessing safety, tolerability, and efficacy are standard measures in clinical studies in PD subjects.

Subjects will be followed for at least 12 months to ensure that long-term safety and tolerability data can be collected. A special focus will be on local tolerability to ensure sufficient data for the evaluation of long-term local reactions at the infusion sites are being collected.

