8.4.5 Method of Assigning Subjects to Treatment Groups

The original plan in this study was that subjects in Cohort 1 remain on the regimen they received in study ND0612H-006; subjects in Cohort 2 were to be randomized to one of the two treatment regimens (Regimen 1 or 2) at a ratio of 1:1. Following the recommendation of the ND0612H-006 oversight committee, the sponsor decided to discontinue Regimen 2 treatment on 08 December 2016. At that point 12 subjects were included in Regimen 2, and all but 2 subjects (who had already been discontinued at that time) on Regimen 2 were transitioned to Regimen 1. The sponsor decided to further evaluate an optimized daily treatment regimen (Regimen 3) of 16 hr at a rate of 0.75 mL/hr; after Protocol amendment 2, all newly enrolled subjects in Cohort 2 were to receive Regimen 3.

Each subject will receive a unique subject number when study staff enter them into the IWRS after they have provided informed consent. Subjects will retain their assigned subject number for the duration of the study; the subject numbers consist of a 3-digit site number and a 3-digit sequential number (i.e., xxx-xxx). Every subject must provide informed consent before any study procedures are conducted. Every subject that provides informed consent must be entered into the IWRS system regardless of eligibility. All subjects who are consented will also have their data entered into the electronic data capture (EDC) system. Subjects who are screen failures will only need to have limited data entered, including the reason for failing screening.

Subjects will enter the treatment period after all screening procedures (if applicable) and baseline assessments have been performed and eligibility for the study has been confirmed. Enrolled subjects who terminate their study participation for any reason, regardless of whether any study medication was received or not, will retain their screening number and randomization number (if applicable) and the study staff will need to enter the information into the IWRS to discontinue the subject's participation in the study.

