11.1.1 Datasets or Populations Analyzed

The All Enrolled Set will consist of all enrolled subjects. All listings will be produced for the All Enrolled Set.

The Safety Set will consist of all subjects receiving at least 1 dose of study drug (ND0612). The Safety Set will be used for all summaries of safety and tolerability data. In addition, summaries of baseline and demographic data will also be produced for the Safety Set.

The modified Intention-to-Treat (mITT) Set will include all enrolled subjects who have valid efficacy data at baseline and at least once after the baseline. The efficacy analysis will be based on the mITT Set. The mITT Set will be used for all summaries and analyses of efficacy data.

The earlier version of this protocol included a randomization of subjects to Regimen 1 or Regimen 2. Unless stated otherwise, the subjects who received Regimen 2 and were switched to Regimen 1 during the study conduct will be included in the Regimen 1 group.

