11.1.4.3.2 Methods of Analysis

All efficacy summaries and analyses will be produced for the mITT Set.

For the efficacy endpoints, continuous data will be summarized at each protocol scheduled time point, by treatment regimen, using summary statistics. Actual values and changes from Baseline will be presented. All categorical endpoints will be summarized at each protocol scheduled time point, by randomized treatment regimen, using frequency tabulations.

As the primary purpose of this study is to explore the 2 treatment regimens with regards to efficacy and safety and not to perform confirmatory analyses comparing the treatment

regimens, there will be no formal hypothesis testing performed and adjustments for multiplicity are not required.

The change from Baseline to Month 12 and to the other visits within each treatment regimen in daily "ON" time without troublesome dyskinesia will be estimated using a Mixed Model for Repeated Measures (MMRM) including response data from all scheduled post-baseline visits with no imputation for missing data. The changes from Baseline within each treatment regimen and the comparison between the Regimens will be estimated, separately for each scheduled study visit, from the same MMRM using contrasts. The treatment regimen (Regimen 1 or Regimen 3, when applicable), visit and the interaction between treatment regimen and visit (if applicable) will be included as fixed factors in the MMRM together with the baseline value as covariate. The analysis for the "ON/OFF" home diary, will be performed only for cohort 2. Changes from baseline will be summarized also the overall data. There will be no random effects. An unstructured covariance structure will be assumed, and the denominator degrees of freedom will be computed using the Kenward-Roger method.

The changes in "ON" time without troublesome dyskinesia will be estimated both as hours (normalized to 16 hours of awake time) and as a proportion out of awake time.

In general, all further efficacy endpoints will be summarized and analyzed using either a MMRM analysis, as described above, for continuous endpoints or descriptive statistics for categorical endpoints. Sensitivity analyses of efficacy data will be conducted by excluding the subjects who were randomized to receive Regimen 2. The definition of the endpoints and the statistical analyses will be detailed in the SAP.

Data collected in the extension period will be analyzed similarly as for the 12-month period.

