3.4. Treatment Assignment & Blinding

This study investigates three dosing regimens of ND0612:

- Regimen 1 – ND0612 solution will be infused subcutaneously via 2 infusion sites for 24 hours continuously. Dosing will start at any time during the day which is convenient for the subject. The regimen will be comprised of two infusion rates: a fixed rate of 0.08mL/h for 6 hours (22:00-4:00-low night rate), which will then change automatically to a rate of up to 0.64 mL/h for 18 hours (4:00-22:00 high day rate). The dose will be delivered via two infusion sites in parallel, utilizing a pump system. The total infusion volume during a 24 hr period will be up to 12.00 ml (~6.00 ml from each infusion site) and deliver 720 mg LD and 90 mg CD.
- Regimen 2 – ND0612 solution will be infused subcutaneously via 2 infusion sites for 14 hours continuously. Dosing will start upon waking. The infusion will be set to a rate of 0.64 mL/h for 14 hours (high rate) from two infusion sites in parallel, utilizing a pump system. The total infusion volume during the infusion period will be up to 8.96 ml (4.48 ml from each infusion site) which is equivalent to delivery of 537.6 mg LD and 67.2 mg CD over the course of 14 hours. On 08 December 2016 the Sponsor made a decision to discontinue treatment Regimen 2

and switched all subjects who were receiving Regimen 2 to Regimen 1 at their next scheduled visit.

[figure not shown]
- Regimen 3 – ND0612 solution will be infused subcutaneously via 2 infusion sites for 16 hours continuously. Dosing will start upon waking. The infusion will be set to a rate of 0.75 mL/h for 16 hours from two infusion sites in parallel, utilizing the pump system. The total infusion volume during the infusion period will be up to 12 ml (6 ml from each infusion site) which is equivalent to 720 mg LD and 90 mg CD.

On 08 December 2016 (Amendment 1), the Sponsor decided to switch all subjects who were treated with Regimen 2 to Regimen 1. Following this decision, ongoing subjects treated with Regimen 2 were to be switched at their next scheduled study visit to Regimen 1. Ongoing subjects in cohort 1 who were treated with Regimen 2 were to be switched at their next scheduled study visit to Regimen 1. Subjects in cohort 2 who were not yet randomized were to be allocated to Regimen 1 instead of being randomized.

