4.1. All screened subjects

This Analysis set consists of all patients who underwent screening and will be used for summary of disposition and data listings.

4.2. Intention-to-Treat (ITT):

The ITT set will include all subjects who were randomized (before Amendment 1) or enrolled (after Amendment 1) to the study. The subjects will be grouped according to the randomized (before Amendment 1) or allocated (after Amendment 1) treatment regimen.

4.3. Safety Set:

The Safety Set will consist of all subjects (cohort 1 and cohort 2) receiving at least 1 dose of study drug (ND0612). The subjects will be grouped according to the treatment regimen actually received. The Safety Set will be used for all summaries of safety and tolerability data.

4.4. Modified Intention-to-Treat (mITT) Set:

The mITT is a subset of the ITT analysis set. The mITT Set for cohort 2 will include subjects having ON/OFF Home diary data at baseline and at least one valid post-baseline measurement. The mITT Set for in cohort 1 will include subjects having UPDRS (part III) efficacy data at baseline and at least one valid post-baseline UPDRS (part III) measurement. The subjects will be grouped according to the randomized (before Amendment 1) or allocated (after Amendment 1) treatment regimen. The mITT Set will be used for all summaries and analyses of efficacy data.

Unless stated otherwise, the subjects who received Regimen 2 and were switched to Regimen 1 during the study will be included in the Regimen 1 group. However, sensitivity analyses will be conducted by excluding the subjects who were randomized to receive Regimen 2, as specified later in this SAP.

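### The Regimen 2 exclusion analysis is limited to GOOD ON time, so daily OFF time and the OFF responder rate in the Regimen 1 group have no direct check

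*SAP*

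**What the plan says.** **Grouping.** SAP 4.4 (modified Intention-to-Treat Set) sets this default: "the subjects who received Regimen 2 and were switched to Regimen 1 during the study will be included in the Regimen 1 group". Protocol 11.1.1 has the same rule. Neither removes the assessments made while the subject was still on Regimen 2.

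**Protocol safeguard.** Protocol 11.1.4.3.2: "Sensitivity analyses of efficacy data will be conducted by excluding the subjects who were randomized to receive Regimen 2". No endpoint is named.

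**SAP version of the safeguard.** SAP 4.4 announces exclusion analyses to be specified later. The later specification is in SAP 8.1, which ends: "These analyses will be done for the “ON” time without troublesome dyskinesia". Daily OFF time (SAP 8.2.2), the OFF responder rate (8.2.4) and morning OFF (8.2.13) carry no Regimen 2 exclusion.

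**Why Regimen 2 was dropped.** Protocol 8.2 reports interim data from study ND0612H-006 suggesting that Regimen 2 was "suboptimal in respect to the therapeutic response as reflected by the daily" OFF time.

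**How many, and when.** Protocol 8.4.5: "At that point 12 subjects were included in Regimen 2, and all but 2 subjects" were moved to Regimen 1; those two had already discontinued. On timing, SAP 3.4 says that "ongoing subjects treated with Regimen 2 were to be switched at their next scheduled study visit to Regimen 1".

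**Missing responder data.** SAP 3.2.3.7 replaces a missing OFF time with the last available value.

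**The concern.** The efficacy analysis estimates the change from baseline within Regimen 1 and within Regimen 3, and the difference between them, visit by visit. Any diary completed on Regimen 2 but tabulated as Regimen 1 makes that visit's Regimen 1 estimate a mixture of two regimens. The protocol foresaw this and planned an exclusion analysis. The SAP keeps it for GOOD ON but not for OFF time, the endpoint the sponsor cited when it discontinued Regimen 2.

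At stake is whether a reader of the study report can tell if the Regimen 1 OFF-time change, the OFF responder rate and the Regimen 1 versus Regimen 3 contrast depend on data recorded under a discontinued regimen. For the responder rate the route to Month 12 is direct: if a subject's last available OFF value was recorded on Regimen 2, the carry-forward rule makes it a Month 12 result.

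**Working it through.** **1. Doses in the plan** (Protocol 8.4.7, Table 2; LD concentration 60 mg/mL)
- Regimen 1: 0.08 × 6 + 0.64 × 18 = 12.00 mL; × 60 = 720 mg LD. Reproduces.
- Regimen 2: 0.64 × 14 = 8.96 mL; × 60 = 537.6 mg LD. Reproduces.
- Infused LD only: 537.6 / 720 = 0.747, so Regimen 2 is 25.3% lower.
- Regimen 2 also schedules 150 mg oral LD each morning: 537.6 + 150 = 687.6 mg; 687.6 / 720 = 0.955, nominally 4.5% lower. Further oral LD as needed is allowed in both regimens.

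The dose gap alone therefore says little about the size of an OFF-time difference. The regimens also differ in infusion duration (24 h against 14 h).

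**2. Subjects**
- On Regimen 2 at discontinuation: 12. Already stopped: 2. Switched: 12 − 2 = 10.
- The diary models use Cohort 2 only (SAP 8.2.1). Regimen 2 was also in use in Cohort 1 (Protocol 8.1.1), and the 12 are not split by cohort. The number in the diary analyses is therefore at most 12.
- The two who stopped on Regimen 2 were never switched, so the grouping rule does not place them, although the summaries offer only Regimen 1 or Regimen 3.

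**3. Visits.** Diaries cover the 2 days before the visit (Protocol 10.2.1.1), and the switch took place at the next scheduled visit. Where a diary was due at the switch visit, it was still recorded on Regimen 2. The documents do not say which visits these were.

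**4. What GOOD ON can show about OFF.** Waking time is normalized to 16 h (SAP 3.2.3.1), so for each diary:

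OFF + GOOD ON + ON with troublesome dyskinesia = 16 h

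change in OFF = −(change in GOOD ON + change in troublesome ON)

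Excluding the Regimen 2 subjects from GOOD ON reveals the OFF effect only if troublesome ON is unaffected. It does not test the 50% OFF threshold.

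**5. Illustrative size (inputs assumed, not from the documents).** Let k be the Cohort 2 subjects still on Regimen 2 at a given diary, n1 the subjects truly on Regimen 1, and d the true OFF difference between the regimens in hours.

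shift in the Regimen 1 visit mean = k / (k + n1) × d

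| k | n1 | share | d = 0.5 h | d = 1 h | d = 2 h |
|---|---|---|---|---|---|
| 3 | 40 | 0.070 | 0.03 | 0.07 | 0.14 |
| 6 | 30 | 0.167 | 0.08 | 0.17 | 0.33 |
| 6 | 12 | 0.333 | 0.17 | 0.33 | 0.67 |
| 10 | 20 | 0.333 | 0.17 | 0.33 | 0.67 |
| 12 | 12 | 0.500 | 0.25 | 0.50 | 1.00 |

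The range is 0.03 to 1.0 h. The top end needs all 12 subjects to be in Cohort 2, on Regimen 2 at the same diary visit, and as numerous as the true Regimen 1 subjects.

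**The case against.** The strongest reply is that the SAP used a discretion the protocol gave it. The protocol speaks of efficacy data, not of every endpoint, and leaves the detail of the analyses to the SAP; GOOD ON is the first-listed efficacy endpoint. This stands as far as it goes: the SAP may choose the endpoints. It does not explain leaving out the one endpoint on which Regimen 2 had been judged.

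Other points also stand:
- Efficacy is exploratory, with nominal p-values and no confirmatory comparison. The Regimen 1 versus Regimen 3 contrast is not randomized in any case, because Regimen 3 was allocated sequentially after Amendment 2.
- The OFF endpoints are defined at Month 12, by which time ongoing subjects would have switched. Influence at Month 12 needs later data to be missing.

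A reader might also infer more than the documents support:
- *That efficacy is treated less strictly than safety, so Regimen 2 records should be dropped from the main model.* The exclusion in SAP 7.1 is an additional safety analysis. The main safety tables keep those data, as the main efficacy analysis does.
- *That OFF time has no check at all.* GOOD ON is a partial one (working, step 4).
- *That Months 1, 3 and 6 are biased in favour of Regimen 3 by a known amount.* The affected visits are not stated, and the size cannot be derived. The direction rests on interim data from another study that only suggested inferiority on OFF time, and says nothing about the other scales.
- *That SAP section 10 is wrong to declare no changes.* That statement refers to protocol V9.0. The protocol available is V10.0, so the text of V9.0 cannot be checked.

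**Conclusion.** The point holds as a gap in the sensitivity analysis of exploratory endpoints. Switched Regimen 2 subjects are analysed as Regimen 1, and the exclusion analysis that would show whether this matters is confined to GOOD ON. Daily OFF time and the OFF responder rate have no direct check; the same is true of morning OFF.

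At most 12 subjects are concerned, 10 of them switched. The bias, if any, cannot be computed because the cohort split, the size of the Cohort 2 Regimen 1 group, the affected visits and the true difference between regimens are not given. The 0.03 to 1.0 h range depends entirely on the assumed inputs and shows only that the effect could be negligible or noticeable. The primary safety analysis is not affected. This is a cheap improvement, not a flaw that undermines the study.

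**What to change.** In SAP 8.1, replace the restriction to GOOD ON with a list:
- Run the exclusion analysis for GOOD ON, daily OFF time, the 50% OFF responder rate and morning OFF and, where programs allow, for the other endpoints analysed with the mixed model.
- Define the excluded group as all subjects who received any Regimen 2 dose in this study. This covers Cohort 1 subjects, who continued a regimen rather than being randomized here, and the two who discontinued on Regimen 2.
- In the responder analysis (SAP 3.2.3.7), do not carry a diary value recorded on Regimen 2 forward as a Month 12 Regimen 1 result.

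Leave the main mixed model unchanged. If the sponsor prefers to keep the restriction, it should state the reason in SAP section 10.

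The cost is one filter on programs already planned, a few more sensitivity tables, and a slightly smaller Regimen 1 group in those tables.
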